12.8.2. Protocol Changes for Amendment 02 (29-JUN-2017) from Amendment 1 (13-Apr-2017)

Where the amendment applies

This protocol amendment is applicable to all sites.

Current and Previous Protocols:**Summary of Changes and Rationale for Amendment No. 2**

Section	Section Title	Change	Rationale
4.2	Treatment Periods and Duration	The Fasting requirement for Day 1 and Day 15 was removed.	Subjects are required to fast on Day 14 and Day 28 only.
12.4.3	Definition of Cardiovascular Events	Appendix 12.4.3- Definition of Cardiovascular Events has been removed from the Protocol Amendment No. 02.	The collection of Cardiovascular Events is not applicable to the 205712 study.

List of Specific Changes

Text which has been deleted from the protocol is indicated in Appendix 12 by ~~strike through~~ format.

Modified text incorporated into this protocol amendment (Protocol Amendment No. 2):**Section 4.2: Treatment Periods and Duration****Rationale for change:**

Subjects are required to fast on Day 14 and Day 28 only.

REVISED TEXT:

Paragraph 4 Sentence 1

On Day 1, following completion of the required pre-dose measurements, the investigator or authorized study unit personnel will administer a single oral dose of 30 mg CAB to each subject ~~under fasting conditions~~ in the unit.

Paragraph 6 Sentence 1

On Day 15 following the completion of the required Day 14 safety assessments and PK collection, subjects will proceed to Period 2, where site staff will administer a single dose of RBT 300 mg and a single dose of CAB 30 mg ~~after an overnight fast of at least 6 hours~~ in the unit. Subjects will be discharged and dispensed a bottle of RBT and a bottle of CAB to be taken at home on Days 16-20.

Section 12.4.3: Definition of Cardiovascular Events

Rationale for change:

The collection of Cardiovascular Events is not applicable to the 205712 study.

REVISED TEXT:

~~12.4.3. Definition of Cardiovascular Events~~

~~Cardiovascular Events (CV) Definition:~~

~~Investigators will be required to fill out the specific CV event page of the CRF for the following AEs and SAEs:~~

- ~~• Myocardial infarction/unstable angina~~
- ~~• Congestive heart failure~~
- ~~• Arrhythmias~~
- ~~• Valvulopathy~~
- ~~• Pulmonary hypertension~~
- ~~• Cerebrovascular events/stroke and transient ischemic attack~~
- ~~• Peripheral arterial thromboembolism~~
- ~~• Deep venous thrombosis/pulmonary embolism~~
- ~~• Revascularization~~

1. INTRODUCTION

The purpose of this reporting and analysis plan (RAP) is to describe the analyses to be included in the Clinical Study Report for Protocol 205712:

Revision Chronology:		
GSK Document No.: 2016N269788_00	23-FEB-2017	Original
GSK Document No.: 2016N269788_01	13-APR-2017	The purpose of this protocol amendment is to update Appendix 12.5.1." Modified List of Highly Effective Methods for Avoiding Pregnancy in Females of Reproductive Potential(FRP)". The updates include clarifying true abstinence for this study and the deletion of double barrier method: condom and occlusive cap (diaphragm or cervical/vault caps) plus spermicidal agent foam/gel/film/cream/suppository) as a highly effective method for avoiding pregnancy in females of reproductive potential (FRP)
GSK Document No.: 2016N269788_02	29-JUN-2017	Clarify the required days for fasting (Day 14 and Day 28). Remove Appendix 12.4.3- Definition of Cardiovascular Events. The collection of Cardiovascular Events is not applicable to the 205712 study.

2. SUMMARY OF KEY PROTOCOL INFORMATION

2.1. Changes to the Protocol Defined Statistical Analysis Plan

There were no changes or deviations to the originally planned statistical analysis specified in the protocol amendment 2 (Dated: 29-Jun-2017).

2.2. Study Objective(s) and Endpoint(s)

Objectives	Endpoints
Primary Objectives	Primary Endpoints

 To compare steady state CAB exposure following 30 mg oral dose once daily with and without RBT 300 mg once daily. 	
 Plasma CAB AUC(0-τ), C_{max}
Secondary Objectives	Secondary Endpoints

 To describe the pharmacokinetic (PK) of CAB 30 mg oral dose once daily administered alone and co-administered with RBT. 	
 Plasma CAB C_t, t_{max}, t_{1/2} and CL/F

 To assess the safety and tolerability of CAB 30 mg oral dose administered alone and in combination with RBT 300 mg once daily. 	
 Safety and tolerability parameters, including adverse events, concurrent medication, clinical laboratory screens, electrocardiogram (ECG), and vital signs assessments.

AUC_(0-t) = area under the plasma concentration time curve from time zero to the last quantifiable time point C_{max} = maximum observed concentration C_t = last quantifiable concentration t_{max} = time of maximum observed concentration t_{1/2} = the elimination half-life CL/F = apparent oral clearance
	

2.3. Study Design

Overview of Study Design and Key Features				
Table 1 Study Design				
Subjects	Screening Period	Period 1 Days 1 – 14	Period 2 Days 15 - 28	Follow-up
N=15	Within 30 Days of Day 1	Treatment A	Treatment B	~10-14 days after last dose of CAB

 • Treatment A = CAB 30 mg once daily x 14 days • Treatment B = RBT 300 mg once daily + CAB 30 mg once daily x 14 days 				
Design Features	This study is a phase I, single-center, open label, fixed-sequence, 2-period crossover study in healthy adults.			
Dosing	
Subjects will undergo a screening visit within 30 days of the first dose of study drug, followed by two treatment periods and a follow-up period.
 
 • Approximately 15 healthy adult subjects will be enrolled to ensure that 12 subjects will complete dosing and critical assessments. • Period 1: Eligible participants will be admitted to the unit on Day -1. Subjects will be dosed for Days 1, 13 and 14 under the fasting conditions in the unit and subjects will be dispensed a bottle of CAB to be taken at home on Days 2-12 and discharged from the unit. Subjects will be provided with a subject diary to document daily recordings of dosing occurring outside of the unit. There will be no washout between Period 1 and Period 2. • Period 2: On Day 15 following the completion of the required Day 14 safety assessments and PK collection, subjects will proceed to Period 2, where site staff will administer a single dose of RBT 300 mg and a single dose of CAB 30 mg after an overnight fast of at least 6 hours in the unit. Subjects will be discharged and dispensed a bottle of RBT and a bottle of CAB to be taken at home on Days 16-20 and 22-25. Subjects will be provided with a subject diary to document daily recordings of home dosing. In the morning of Days 21, subjects will bring their bottle of RBT and bottle of CAB for observed dosing in the unit and safety assessments as an outpatient visit. On Days 26 and 27, subjects will return to the unit for a pre-dose PK collection and observed dosing as an outpatient visit and then be discharged home. In the morning of Day 28 following an overnight fast of at least 6 hours, subjects will receive a single dose of RBT and a single dose of CAB in the unit with serial CAB PK samples collected pre-dose and through 24 hours after dosing up to Day 29. • Subjects will be discharged from the unit on Day 29 after the final assessment is completed. Subjects will complete a follow-up visit ~ 10-14 days after the last 30 mg oral dose of CAB. 			

Overview of Study Design and Key Features	
Treatment Assignment	Subjects will receive following treatments in a fixed sequence of A/B: 
 • Treatment A = CAB 30 mg once daily x 14 days • Treatment B = RBT 300 mg once daily + CAB 30 mg once daily x 14 days
Interim Analysis	
 • No interim analysis will be performed.

2.4. Statistical Hypotheses

No formal hypothesis will be tested. This study is designed to estimate the drug-interaction effect of RBT on CAB PK parameters. An estimation approach will be used to evaluate the effect of RBT on CAB PK. Point estimates and corresponding 90% confidence intervals (CIs) will be constructed for the comparisons of interest (test:reference).

3. PLANNED ANALYSIS

3.1. Interim Analyses

- No interim analysis will be performed.

3.2. Final Analyses

Final analyses will be performed after the completion of the study, following sequential steps and final database authorization:

1. All subjects have completed the study as defined in the protocol.
2. All required database cleaning activities have been completed and final database release and database freeze has been declared by Data Management.
3. All criteria for unblinding the randomisation codes have been met.
4. Randomisation codes have been distributed according to RandAll NG procedures.

4. ANALYSIS POPULATIONS

Population	Definition / Criteria	Analyses Evaluated
Screening Population	All subjects who sign the consent form will be included in this population.	
 Screening population listing and summary
Safety Population	All subjects who enrol in the study and receive at least one dose of study drug will be included in the Safety Population.	
 Study Population Safety
PK Concentration Population	The CAB PK Concentration Population will include all subjects who undergo plasma PK sampling and have evaluable PK assay results.	
 PK concentration listing, and individual concentration plot
PK Parameter Population	The PK Parameter Population will include all subjects who have evaluable PK parameters. Data from subjects who vomit within 4 hours of study drug administration will not be considered as evaluable.	
 PK parameter listing, and plotting
PK Summary Population	The CAB PK Summary Population for this study will include subjects who have CAB PK parameter estimates from both serial PK sampling time periods 1 and 2. These populations will be used for the concentration and PK parameters summary figures and tables and for the statistical analysis of PK parameter data	
 PK concentrations and summary table and summary figures PK Parameter Summary table Statistical analysis of parameter data

NOTES :

- Please refer to [Appendix 11](#) which details the population to be used for each display being generated.

4.1. Protocol Deviations

Important protocol deviations (including deviations related to study inclusion/exclusion criteria, conduct of the trial, subject management or subject assessment) will be listed.

- Protocol deviations will be tracked by the study team throughout the conduct of the study in accordance with the Protocol Deviation Management Plan.
 - Data will be reviewed prior to unblinding and freezing the database to ensure all important deviations and deviations which may lead to exclusion from the PK analysis are captured and categorised on the protocol deviations dataset.
 - This dataset will be the basis for the summaries and listings of protocol deviations.
- A separate summary and listing of all inclusion/exclusion criteria deviations will also be provided. This summary will be based on data as recorded on the inclusion/exclusion page of the eCRF.

5. CONSIDERATIONS FOR DATA ANALYSES AND DATA HANDLING CONVENTIONS

Table 2 provides an overview of appendices within the RAP for outlining general considerations for data analyses and data handling conventions.

Table 2 Overview of Appendices

Section	Component
Section 10.1	Appendix 1 : Protocol Deviation Management
Section 10.2	Appendix 2 : Data Management
Section 10.3	Appendix 3 : Time & Events
Section 10.4	Appendix 4 : Treatment States and Phases
Section 10.5	Appendix 5 : Data Display Standards & Handling Conventions
Section 10.6	Appendix 6 : Derived and Transformed Data
Section 10.7	Appendix 7 : Premature Withdrawals & Handling of Missing Data
Section 10.8	Appendix 8 : Values of Potential Clinical Importance
Section 10.9	Appendix 9 : Model Checking and Diagnostics for Statistical Analyses.
Section 10.10	Appendix 10 : Abbreviations and Trade Marks
Section 10.11	Appendix 11 : List of Data Displays
Section 10.12	Appendix 12 : Example Mock Shells for Data Displays

6. STUDY POPULATION ANALYSES

6.1. Overview of Planned Analyses

The study population analyses will be based on the “Safety” population, unless otherwise specified.

Table 3 provides an overview of the planned study population analyses, with full details of data displays being presented in [Appendix 11](#): List of Data Displays.

Table 3 Overview of Planned Study Population Analyses

Display Type	Data Displays Generated		
	Figure	Table	Listing
Study Population			
Analysis Population Summary		Y	
Subject Disposition			
Subject Disposition		Y	Y

Display Type	Data Displays Generated		
	Figure	Table	Listing
Protocol Deviations		Y	Y
Inclusion and Exclusion Criteria Deviations			Y
Demography			
Demographics Characteristics		Y	Y
Race & Racial Combinations		Y	Y
Age Group Breakdown for Trial		Y	
Others			
Concomitant Medication		Y ¹	Y
Genetic sample collection			Y
Random codes			Y
Treatment non-compliance			Y
Screening information		Y ²	Y ³

NOTES:

- Y = Yes display generated.
- 1. Conditional display, if data contains more than 10 records.
- 2. Screening population.
- 3. All screen failures

7. PRIMARY STATISTICAL ANALYSES

7.1. Pharmacokinetic Analyses

The reconciliation of the PK Case Report Form (CRF) and SMS2000 data will be performed by Data Management, QSci at GlaxoSmithKline.

The merge of PK concentration data, randomization and CRF data will be performed. The analysis PK concentration dataset and WinNonLin files will be created by statistics and programming, under the direct auspices of statistics and programming, Quantitative Sciences (QSci), GlaxoSmithKline.

Derivation of pharmacokinetic parameters will be performed under the direct auspices of Clinical Pharmacology Modelling & Simulation (CPMS), QSci, GlaxoSmithKline.

Statistical Analysis of pharmacokinetic parameters will be performed by statistics and programming under the direct auspices of statistics and programming, QSci, GlaxoSmithKline.

7.1.1. Overview of Planned Pharmacokinetic Analyses

The pharmacokinetic (PK) analyses will be based on the PK Concentration, PK Parameter, or PK Summary populations where it is specified.

Table 4 provides an overview of the planned analyses, with full details being presented in Appendix 11: List of Data Displays.

Table 4 Overview of Planned Pharmacokinetic Analyses

Endpoints	Untransformed				Log _e -Transformed			
	Summary		Individual		Summary		Individual	
	F	T	F	L	F	T	F	L
Plasma Drug Concentrations	Y ^{[1][2]}	Y	Y ^[1]	Y	Y ^{[1][2]}		Y ^[1]	
Derived PK Parameters		Y	Y ^[3]	Y		Y	Y ^[3]	
Statistical Analysis PK Parameters					Y ^[4]	Y		Y ^[5]

NOTES :

- T = Table, F = Figures, L = Listings, Y = Yes display generated.
 - Summary = Represents TF related to any summaries (descriptive statistics) of the observed raw data.
 - Individual = Represents FL related to any displays of individual subject observed raw data.
 - Tmax is not log transformed.
1. Linear and Semi-Log plots will be created on the same display.
 2. Mean (+SD) and Median plots will be generated.
 3. Comparative Plot of Individual CAB Plasma PK Parameter vs treatments on linear and semi-log scale
 4. Geometric Mean Treatment Ratio and 90% CI of CAB Plasma PK Parameters will be generated.
 5. Supportive SAS Output from Statistical Analysis of Log_e-transformed CAB Plasma PK Parameters

7.1.2. Drug Concentration Measures

Refer to Appendix 5: Data Display Standards & Handling Conventions (Section 10.5.3 Reporting Process & Standards).

7.1.3. Pharmacokinetic Parameters

PK analyses will be the responsibility of the CPMS department within GSK or their designee. Plasma CAB concentration-time data will be analyzed by non-compartmental methods according to current working practices and using Phoenix WinNonlin 6.3 or higher. Calculations will be based on the actual sampling times recorded during the study and based on nominal sampling times. From the plasma concentration-time data, the following PK parameters will be determined, as data permit: C_{max}, T_{max}, C_τ, t_{1/2}, AUC(0-τ) and CL/F.

Statistics and Programming group will calculate the individual ratios for C_{max}, C_τ and AUC(0-τ).

Refer to Appendix 5: Data Display Standards & Handling Conventions (Section 10.5.3 Reporting Process & Standards).

Non-compartmental analysis will be performed in accordance with GSK PK Guidance document GUI_51487.

Refer Appendix 7 Section 10.7.2.2 for handling of PK Concentration data.

Table 5 Derived Pharmacokinetic Parameters

Parameter	Parameter Description
AUC(0- τ)	Area under the plasma concentration-time curve at the end of the dosing interval will be calculated using the linear trapezoidal rule for each incremental trapezoid and the log trapezoidal rule for each decremental trapezoid.
C _{max}	Maximum observed concentration, determined directly from the concentration-time data.
C _{τ}	Plasma concentration at the end of the dosing interval
T _{max}	Time to reach C _{max} , determined directly from the concentration-time data.
t _{1/2}	Apparent terminal half-life will be calculated as: $t_{1/2} = \ln 2 / \text{Lambda}_z$ (NOTE: Lambda_z is the terminal phase rate constant).
CL/F	The apparent oral clearance (CL/F) will be calculated as $\text{CL/F} = \text{Dose}/\text{AUC}(0-\tau)$

PK parameters that have mass in the units should be reported in $\mu\text{g}/\text{mL}$ and $\text{h}\cdot\mu\text{g}/\text{mL}$ for CAB. CL/F should be reported in units of L/h.

7.2. Statistical Analysis of Pharmacokinetic Parameters

All PK data will be stored in the Archives, GlaxoSmithKline R& D. Statistical analyses of the PK parameter data will be the responsibility of Clinical Statistics, GlaxoSmithKline or their designee.

For each of the parameters C_{max}, C _{τ} , AUC(0- τ), t_{1/2} and CL/F, if data permit, the following summary statistics will be calculated and tabulated by treatment :

- **Untransformed Data :** N, n, arithmetic mean, SD, median, minimum, maximum and %CV.
- **Log_e-transformed Data:** Geometric mean, 95% CI for the geometric mean, SD of log_e-transformed data and %CVb

For T_{max}, the summary statistics specified for untransformed data above will be generated.

Primary and Secondary Comparisons of Interest

	CAB PK Parameter	Test	Reference	Assessment
Primary	C _{max} and AUC(0- τ)	Treatment B: RBT+CAB	Treatment A: CAB	Interaction
Secondary	C _{τ} , t _{1/2} and CL/F	Treatment B: RBT+CAB	Treatment A: CAB	

The PK parameters for CAB (except T_{max}) will be log_e-transformed and separately analyzed using a mixed effects model. Analysis of variance (ANOVA), considering treatment as fixed effect and subject will be treated as a random effect in the model, will

be performed using SAS Mixed Linear Models procedure to evaluate the effect of RBT on CAB PK parameters: AUC(0- τ) and C_{max}. Similar model will be applied for secondary endpoints: C _{τ} , t_{1/2} and CL/F. Point estimates and their associated 90% CIs will be constructed for the differences in PK parameter values between RBT+CAB and CAB alone for the treatment comparisons. The point estimates and their associated 90% CIs will then be back-transformed to provide point estimates and 90% CIs for the ratios of PK parameters between test and reference treatments.

Estimates of within-subject variability for C_{max}, C _{τ} , t_{1/2}, AUC(0- τ) and CL/F will be provided, where $CV_w(\%) = \text{SQRT}(\exp(\text{MSE}) - 1) \times 100$ and MSE is the residual mean squared error from the model. CV_w represents a pooled measure of within-subject variability across the treatments CAB and RBT+CAB.

Pre-dose concentrations collected between Days 13-14 and Days 26-28 will be listed with PK concentration profiles and summarized by Day/Time. To assess for achievement of steady-state of CAB when CAB is given with RBT, Analysis of variance (ANOVA), considering DAY as fixed effect and subject as a random effect in the model, will be performed using SAS Mixed Linear Model on the pre-dose concentration between Days. The estimated slope and 90% CI will be presented for models included 2 days (Days 13-14, 27-28) or 3 days (Days 26-28) pre-dose concentrations.

Comparative Plot of Individual subject CAB Plasma PK Parameter Versus Treatment will be generated.

Individual and box plots of Pre-dose concentration of Day 13-14 and Days 26-28 will be generated.

Plots will also be provided showing the adjusted geometric mean ratio of test to reference treatment for C_{max}, C _{τ} , AUC(0- τ), t_{1/2} and CL/F with 90% CIs.

The SAS output from the statistical models will be included in a listing of supportive SAS output.

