4.2. Treatment Periods and Duration

Subjects will undergo a screening visit within 30 days of the first dose of study drug, followed by two treatment periods and a follow-up period.

Subjects will undergo clinical safety assessments and serial PK assessments at time-points specified in Section 7.1, Time and Events table of the protocol.

Period 1

Eligible participants will be admitted to the unit on Day -1.

On Day 1, following completion of the required pre-dose measurements, the investigator or authorized study unit personnel will administer a single oral dose of 30 mg CAB to each subject in the unit.

Subjects will be dispensed a bottle of CAB to be taken at home on Days 2-12 and discharged from the unit. Subjects will be provided with a subject diary to document daily recordings of dosing occurring outside of the unit. Subjects will be re-admitted to the unit in the morning on Day 13. Prior to dosing, a CAB PK sample will be obtained, and then the subjects will receive a single 30 mg dose of CAB on Day 13 and remain in the unit overnight. On Day 14, following an overnight fast of at least 6 hours, subjects will receive a single 30 mg dose of CAB with serial CAB PK samples collected pre-dose and through 24 hours after dosing up to Day 15. There will be no washout between Period 1 and Period 2.

Period 2

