The duration of dosing in this study was chosen partly based on scientific convention with similar P1 drug-drug interaction studies and particular to this protocol, because of the importance of achieving a steady state concentration of study drug (CAB) before PK analyses of CAB are performed during Period 1 of the study. Similarly, in Period 2 of the study, a similar rationale for duration of 14 days applies to the combination of CAB and RBT as well. Oral CAB has a terminal phase elimination $t_{1/2}$ of approximately 40 hours and reaches steady state by 10-12 days of once daily administration, supporting 14 days of dosing in this study [GlaxoSmithKline Document Number 2012N136689_00, LA1116585]. Before obtaining PK assessments, both CAB and RBT need to reach steady state and 14 days is sufficient time for that to occur.

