9.4.2. Secondary Analyses

Safety data will be presented in tabular and/or graphical format and summarized descriptively according to GSK's Integrated Data Standards Library (IDSL) standards.

The point estimates of the geometric least squares (GLS) mean ratio for the PK parameters C_{τ} , $t_{1/2}$ and CL/F and the associated 90% CIs will be provided for treatment comparisons (test:reference). The PK parameters will be log-transformed prior to analysis and treatment comparisons will be expressed as ratios on the original scale as

primary PK parameter. Plasma tmax will only be summarized with the descriptive statistics.

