5. A serum pregnancy test will be performed at the screening visit and a urine pregnancy test at all other time points specified.
6. Duplicate ECG, BP, and HR assessments will be conducted pre-dose on Day 1. Single measurements will be collected at all other time points.
7. Study medication will be administered with 240 mL of water within the unit on Days 1, 13, 14, 15, 21, 26, 27, and 28. Dosing on non-PK days may be with or without food, but dosing on serial PK days (Day 14 in Period 1 and Day 28 in Period 2) must be after an overnight fast of at least 6 hours, and no food will be allowed for 4 hours after dosing on these serial PK days.
8. Dispense the bottle of CAB tablets to the subject on Day 1 to receive CAB dosing at home on Days 2 to 12 in Period 1
9. Dispense the bottle of CAB tablets to the subject on Day 15 to receive CAB dosing at home on Days 16 to 20 and Days 22 to 25 in Period 2; dosing on Day 21, 26, 27, and 28 is in the unit.
10. Dispense the bottle of RBT capsules to the subject on Day 15 to receive RBT dosing at home on Days 16 to 20 and Days 22 to 25 in Period 2; dosing on Day 21, 26, 27, and 28 is in the unit.
11. Plasma PK samples (2 mL of blood per sample) will be collected to measure CAB at the following time points: Period 1: predose (within 15 minutes prior to dose) on Day 13; and pre-dose (within 15 minutes prior to dose), 1, 2, 3, 4, 8, 12, and 24 hours after CAB dosing on Day 14. Period 2: pre-dose (within 15 minutes prior to dose) on Days 26 and 27 and pre-dose (within 15 minutes prior to dose) on Day 28 and, 1, 2, 3, 4, 8, 12, and 24 hours after CAB +RBT dosing on Day 28.
12. It is recommended that the Pharmacogenetic sample be collected on Day 1, but it may be collected at any time following administration of investigational product.

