10.9. Appendix 9: Model Specifications for Statistical Analysis

10.9.1. Statistical Analysis Assumptions and Model Specifications

Endpoint(s)	C _{max} , C _τ , AUC(0-τ), t _{1/2} and CL/F, if data permitted
Analysis	Linear Mixed Model

Specifications:
 
 For the Linear Mixed Model, model assumptions will be PK parameter following log-normal distribution. For drug-drug interaction assessment, an example of SAS code is included here. <pre>Proc Mixed; By parameter; class treatment subject; model logPKpar = treatment/ddfm=kr outpred=pred; random subject; lsmeans treatment; estimate 'B:A' treatment -1 1/cl alpha=0.1; /* (CAB+RTB) vs (CAB alone) */ run;</pre> 
 An example of SAS code to assess achievement of steady-state is included here. <pre>Proc Mixed; by dose; where day in (13,14); class subject; model logC0 = day/ddfm=kr cl alpha=0.1 solution; random intercept/subject=subject type=un solution; make 'solutionf' output=stat; run;</pre> 
repeat for Days 26,27,28 and Days 27,28
	

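### Should t1/2 lose its treatment ratio and 90% CI because each period is sampled for only 24 h?

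*SAP*

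**What the plan says.** SAP 7.2 fits a log-scale mixed model (treatment fixed, subject random) to AUC(0-τ) and Cmax and then states "Similar model will be applied for secondary endpoints", naming Cτ, t1/2 and CL/F. The back-transformed difference gives a ratio with a 90% CI. A within-subject CV is also reported for t1/2, and the ratio is plotted: "Plots will also be provided showing the adjusted geometric mean ratio of test to reference treatment for" all five parameters. Protocol 9.4.2 plans the same secondary comparison.

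Table 5 of SAP 7.1.3 gives the definition: "Apparent terminal half-life will be calculated as" ln 2 divided by Lambda_z, the terminal-phase rate constant. Footnote 11 of the Time and Events table (SAP Appendix 3) schedules a pre-dose sample and then "1, 2, 3, 4, 8, 12, and 24 hours after CAB dosing on Day 14", with the same times on Day 28. Protocol 4.2 adds: "There will be no washout between Period 1 and Period 2". The Day 15 dose therefore closes the Day 14 profile at 24 h.

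Protocol 4.5 puts the terminal half-life at a value "of approximately 40 hours and reaches steady state by 10-12 days of once daily administration", and cites single-dose studies that sampled for 168 h. Derivation of t1/2 is conditional on the data supporting it, and SAP 7.1.3 refers the non-compartmental analysis to an internal guidance document that is not in the public set.

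**The concern.** A terminal slope is usually read from a span of more than one half-life. Here the whole window is 0.6 of a half-life, and the 8, 12 and 24 h samples span 0.4, over which a 40 h half-life gives a fall of only about 24%. Small assay or timing errors then move the slope a good deal, and some of the decline seen within 24 h may still be distribution.

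Two things would be at stake. First, a number labelled as terminal half-life might understate it, and could be set beside the 57% fall in terminal t1/2 quoted for rifampin in Protocol 2.1. Second, its interval might be much wider than the one the study was sized to give. One response would be to report t1/2 descriptively only, with no ratio and no CI.

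**Working it through.** **Inputs.** Half-life 40 h (Protocol 4.5); sampling times (SAP Appendix 3); 12 evaluable subjects and within-subject CV 11.4%, or 22.8% in the sensitivity case (Protocol 9.2.1 and 9.2.2); single-dose AUC(0-∞) 174 and 141 μg·h/mL with Cmax 4.24 and 3.70 μg/mL (Protocol 4.5). The documents give no residual error for a single concentration, so 3%, 5% and 10% are assumed.

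**1. The plan's own figure.** Half-width = t(0.95, 11) × √ln(1+CV²) × √(2/12) = 1.796 × 0.1136 × 0.408 = 0.0833, so the interval is 0.92–1.09, as stated for AUC(0-τ) and Cmax. At CV 22.8% the same formula gives 0.165, or 0.85–1.18. (The protocol's 16.7% comes from using the CV itself as the log-scale SD.)

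**2. Window.** k = ln 2/40 = 0.01733 per hour. 24/40 = 0.60 and 16/40 = 0.40; the fall over 8–24 h is 1 − exp(−16k) = 24.2%.

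**3. Precision.** For 8/12/24 h, √Sxx = 11.78 h, so the CV of one subject's Lambda_z is σ/(k × 11.78) = σ/0.204. Simulated trials (20,000 per error level, 12 paired subjects, one-compartment decline, true ratio 1) gave:

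| Assumed residual error | CV of one slope, 8/12/24 h | Median 90% CI, 8/12/24 h | Narrowest with 4/8/12/24 h or best-fit selection |
|---|---|---|---|
| 3% | 14.7% | 0.90–1.11 | 0.92–1.09 |
| 5% | 24.5% | 0.83–1.21 | 0.87–1.15 |
| 10% | 49.0% | 0.65–1.53 | 0.73–1.37 |

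A fixed fit from 3 h onward is slightly narrower again (about 0.88–1.13 at 5%). Coverage was 0.90–0.91 and the ratio was unbiased. The t1/2 interval becomes wider than 0.92–1.09 once residual error passes 0.1136 × 0.204 = 2.3% (8/12/24 h) or 2.9% (4/8/12/24 h). It becomes wider than 0.85–1.18 past 4.6% or 5.8%. Occasion-to-occasion variation would add to this.

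**4. Direction of bias in the absolute value.** Under one-compartment decline, Cmax cannot exceed AUC × k: 174 × 0.01733 = 3.02 and 141 × 0.01733 = 2.44. The reported values are 4.24/3.02 = 1.41 and 3.70/2.44 = 1.51 times these, so the protocol's figures imply a faster early phase. Two-compartment profiles matched to those AUC and Cmax values with a terminal 40 h (assumed ka 0.7–4 per hour, k21 0.05–0.4 per hour) give an 8–24 h half-life of 24–40 h, with a median of about 35 h. Slow absorption reverses the direction: a one-compartment profile with ka 0.3 per hour gives 45 h from 8–24 h.

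**5. Bias in the ratio.** In the same profiles, with 14 further daily doses after clearance rises by 25%, the window ratio is 0.80–0.82 against a terminal ratio of 0.80–0.84. Window divided by terminal is 0.96–1.00. For a 2.4-fold rise, as quoted for rifampin, it is 0.79–1.01.

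**6. Can the interval still inform?** With a true ratio of 0.43 (a 57% fall), one-compartment decline and 8/12/24 h, the median 90% CI is about 0.39–0.46, 0.37–0.48 or 0.29–0.54 at 3%, 5% or 10% error. Its upper limit was below 1 in every simulated trial.

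**The case for a change.** The best case for a change is about the label. Correct coverage is coverage for a within-interval slope, while the table heading says terminal half-life. Neither the word apparent in Table 5 nor the proviso about the data sets a window, a number of points or a fit criterion, and no guidance document can add samples after 24 h. The near-cancellation of bias in the ratio also depends on a modest effect. Protocol 4.5 contemplates a 70–80% reduction in exposure, and at a 2.4-fold clearance rise the window ratio can fall to 0.79 of the terminal ratio.

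Much of this stands. The estimate is a within-interval slope, and a report that set it beside the rifampin figure without saying so would mislead. But the objection is strongest against the absolute half-life, which a descriptive-only summary would keep. SAP 7.2 already tabulates geometric means by treatment, so readers could still form a ratio, now without the within-subject interval that shows how uncertain it is. Extra samples are not available in Period 1 without breaking the continuous dosing. An effect large enough to distort the ratio would show directly in AUC(0-τ), Cτ and CL/F, none of which uses Lambda_z. The comparison with 0.92–1.09 also has limited force, because Protocol 9.2 sizes the study on AUC(0-τ) and Cmax only.

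**Conclusion.** No change to the plan. Reporting a ratio and CI for t1/2 from a 24 h window is a fair trade-off in an estimation study with no hypothesis test. The interval shows the imprecision honestly, and the ratio is the better-supported of the two quantities. The absolute half-life may be understated (24–40 h for a true 40 h, under assumed two-compartment parameters), while the ratio stays within about 4% of the terminal ratio for a 25% rise in clearance.

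How wide the interval will be is not known, because the documents give no residual error: with 8/12/24 h sampling and a true ratio of 1 it runs from 0.90–1.11 at 3% to 0.65–1.53 at 10%. The coverage result assumes one-compartment decline, and the bias result assumes the modest induction that the protocol expects. The interaction conclusion rests on AUC(0-τ) and Cmax and is untouched. Noting the 24 h span beside the t1/2 results is ordinary reporting practice that needs no amendment, since Table 5 already calls the half-life apparent and the SAP makes its derivation conditional on the data.
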